Cover page for clinical trials.gov

Official Study Title: Socio-Structural Intervention to Improve Pre-Exposure Prophylaxis Services for Cisgender Women (PrEP CGW)

NCT number: pending

Date of Document: May 3, 2021

STATISTICAL DESIGN & POWER

Aim 1: Intervention Development. We will recruit n=10 key informants for in-depth interviews and up to n=60 CGW and medical providers to contribute to the focus groups (2-3 groups per population with groups of 8-10 participants) and theater testing.

Aim 2: Feasibility Trial. Given the pilot nature of this study, it is not appropriate to conduct a power analysis; We are not testing effectiveness during this stage of the trial.¹

Measures & Analysis. Data collection will be ongoing in through the EMR; reach and initial effects data will be extracted for all CGW at three time points (baseline, intervention, and discontinuation). More detailed data in regard to the intervention strategies (provider training and peer navigation) will be collected on Adoption and Implementation (feasibility and acceptability) at the end of the intervention time period as described in **Table 1** below.

Table 1. Aim 2 Outcomes, Data Sources, and Time Points for Evaluation

Outcome	Data Source/ Measure	Time of Evaluation*
Reach (also shows feasibility of intervention)		
% of eligible CGW counseled on PrEP by providers	EMR	Year 3, Quarter 2 (End of Intervention)
% of CGW who complete HIV prevention discussion with peer navigator	Comparison of peers' patient log with EMR patient visit log	Year 3, Quarter 2
Measure of Initial Effects (note: no statistical testing for effectiveness in pilot phase; measures are for feasibility of data collection and standard deviation calculation)		
% change in perceived medical bias	7-item Discrimination in Medical Settings Scale	Year 2, Quarter 3 & Year 3 Quarters 1&2
% eligible CGW initiate PrEP	EMR	Year 3, Quarter 2
Of CGW who initiate PrEP, % adherence at 1 month	EMR, DBS**, & Pharmacy Data	Year 3, Quarter 2
Of CGW who initiate PrEP, >75% will persist \geq 1 month	EMR & Pharmacy Data	Year 3, Quarter 2
Adoption		
% of providers who participate in synchronous or asynchronous training	Attendance log	Year 3, Quarter 2
% change in knowledge/awareness of medical bias and positive PrEP counseling techniques	Provider training module pre- & post-knowledge questionnaires	Year 2 Quarter 4- Year 3 Quarter 1
Implementation		

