Perceived feasibility of implementing the intervention	Provider & Peer Likert scale survey & Provider & Peer in-depth interviews (n=10)	Year 3, Quarter 2
Acceptability: % CGW who receive provider counseling or peer session and report high satisfaction	CGW; Likert scale survey to rate affective attitude, or feelings towards the intervention, burden, or perceived amount of effort to participate, and congruence with individual values ²	Year 3, Quarters 1-2 (Post-clinical visit or peer session)
Satisfaction with training (synchronous vs. asynchronous) and outreach intervention among providers and peers	Provider & Peer Likert scale survey; Provider & Peer in-depth interviews (n=10)	Year 2 Quarter 4 - Year 3 Quarter 2 (Beginning, mid, & end of intervention) Year 3, Quarters 1-2
Organizational perspective on the intervention	Provider & Peer in-depth interviews (n=10)	Year 3, Quarters 1-2
Patient perspective on the intervention	Patient in-depth interviews (n=20)	Year 3, Quarters 1-2

*See **Study Timeline** in PHS

For percentage outcomes we will use the following “traffic light” benchmark system for feasibility and acceptability in Aim 2: 0-50%: failure of the current intervention design; 51-75%: major revisions required; 76%: no or minor revisions needed for a confirmatory trial.

Questionnaires. RAs will invite all CGW seen in FPPC to participate in a 5-minute tablet-based survey to assess acceptability of the provider and peer components of the intervention and intention to initiate PrEP; CGW seen virtually will be contacted by phone and/or email and invited to participate in an online survey. We anticipate that approximately 300 CGW will complete the survey. Upon survey completion, participants will be invited to provide their contact information to participate in virtual or in-person IDI. Additionally, to assess intermediate effects of the provider trainings, we plan to use the 7-item Discrimination in Medical Settings Scale³, which has been validated in Black populations, to capture changes in patient-reported experiences before and after implementation of trainings to capture participant perceptions of bias.

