Quantitative data will be entered into REDCap for structured data storage and analyzed using Python/R language. We will conduct a descriptive summary of the outcomes described in the above Table 1. Where appropriate, we will test item scale reliability using the intraclass correlation coefficient (ICC). In surveys we will also collect data on demographics (e.g., race, age, education, income, partner status), behavioral risk for HIV (e.g., number of sexual partners, HIV status of partner, consistency of condom use), medical history (e.g., comorbidities, duration of risky behaviors), and lifestyle habits (e.g., smoking, alcohol consumption, substance abuse). We will also describe the demographic and clinical characteristics of CGW included in the sample, including means (standard deviations) or medians (interquartile ranges), and frequencies (percentages). Following descriptive statistics, we will compare the proportions of CGW who initiate PrEP and persist ≥ 1 month by key characteristics (e.g., age, partner status). We will use logistic regression to explore characteristics of those initiating PrEP and continuing past one month.

In order to better estimate treatment standard deviations, we will explore RDD analyses in preparation for our future effectiveness trial. RDD is a quasi-experimental, pretest-posttest design, it is commonly used for causal research studies, which involve distinct cutoff values that assign subjects into different conditions and compare different conditions' outcomes. In the full-scale effectiveness trial, we will isolate the treatment effect by designing a baseline period (months 6-9 in year 2) and intervention period (month 12 year 1 to month 3, year 3), and will determine the cutoff points before the data collection. The design allows an unbiased estimate of the treatment effect by minimizing confounding bias and assessing the magnitude of the discontinuity on outcomes at the cutoff point. We will also consider potential confounders of demographics factors including age, income, partner status in the analysis to achieve comparability and exchangeability.

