Capperlieri et.al. conducted a power analysis using $\alpha = .025$ (one-tailed) and provided recommendations for the sample sizes for detecting different standardized effect sizes.⁷ Their results show: 1) a sample of 1078 would have a power of .80 for detecting a small effect size, 2) a sample of 150 would have a power of .80 for detecting a medium effect size, 3) a sample of 68 would have a power of .80 for detecting a large effect size, and 4) a sample size of 109 would have power of .95 for detecting a large effect size. While we are not conducting effectiveness testing at this stage, our numbers should allow for calculation of standard deviations to prepare for our fully powered trial. Based on their study, we will recruit an adequately sample size of CGW participants for the preliminary RDD analysis (i.e., 460 CGW participants during the intervention period, an additional 345 CGW participants in the baseline, and 460 in the discontinuation period).

[name] will conduct analyses in PythonR⁸. All data reporting will follow the CONsolidated Standards of Reporting Trials (CONSORT) guidelines.⁹

5. ATLAS.ti: The Qualitative Data Analysis & Research Software. Accessed January 7, 2021. <https://atlasti.com/>

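### Does naming income and partner status as RDD confounders, with survey data on about 300 women against 1,265 in the RDD, require a change to the plan?

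*SAP*

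**What the plan says.** All of this stands in the SAP, under Aim 2.

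- **RDD paragraph.** The RDD is to be explored so that standard deviations are better known for a later trial. The paragraph then describes the full-scale trial, its baseline and intervention periods and its cutoffs, and ends: "We will also consider potential confounders of demographics factors including age, income, partner status in the analysis to achieve comparability and exchangeability".
- **RDD sample-size paragraph.** The preliminary analysis is to use "460 CGW participants during the intervention period, an additional 345 CGW participants in the baseline, and 460 in the discontinuation period".
- **Quantitative data paragraph.** The source of the covariates is given as "In surveys we will also collect data on demographics (e.g., race, age, education, income, partner status" and further items. The same paragraph compares PrEP initiation and persistence "by key characteristics (e.g., age, partner status" and similar).
- **Questionnaires.** For the tablet or online acceptability survey: "We anticipate that approximately 300 CGW will complete the survey". Table 1 times the acceptability measure at "Year 3, Quarters 1-2 (Post-clinical visit or peer session"). The Discrimination in Medical Settings Scale is also given to patients "to capture changes in patient-reported experiences before and after implementation of trainings". Table 1 places it in Year 2 Quarter 3 and Year 3 Quarters 1 and 2, with no number of respondents.
- **Measures & Analysis.** From the electronic medical record (EMR), "reach and initial effects data will be extracted for all CGW at three time points (baseline, intervention, and discontinuation"). Demographic items are not listed for this extract, and nothing says that they are absent from it.

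**The concern.** A covariate helps an RDD only if it is measured in the same way on both sides of the cutoff. Read literally, the SAP names two confounders, gives one source for them, and sizes that source at under a quarter of the RDD sample. The sized survey falls in the intervention period, after a visit or peer session. The plan gives no coverage by period and no rule for women without the covariates.

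If an analyst added income and partner status and kept complete cases only, the adjusted result would describe women who chose to answer a survey after exposure. The unadjusted result would describe all CGW. The adjusted result would also be less precise. If willingness to respond were related to PrEP initiation, and that relation differed across the cutoff, the adjustment could introduce bias. The results are meant to inform the design of a larger trial, so this deserved a check.

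**Working it through.** **Inputs.** Baseline 345, intervention 460 and discontinuation 460 (RDD sample-size paragraph); about 300 survey completers (Questionnaires). The SAP derives none of these, so there is no calculation of its own to reproduce, and it does not print the total.

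**Coverage.**
- Total: 345 + 460 + 460 = 1,265. First cutoff (baseline and intervention): 345 + 460 = 805.
- 300/1,265 = 23.7%, which leaves 965 women without a stated source. 300/805 = 37.3%.
- If all 300 are in the intervention period: 300/460 = 65.2% there and 0/345 at baseline.

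**Precision at the first cutoff, complete cases against all women.** This assumes a simple two-group contrast. The ratio of standard errors is √(1/n_b + 1/n_i) / √(1/345 + 1/460), where the denominator is 0.0712.

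| Where the covariates exist | n_b | n_i | Ratio |
|---|---|---|---|
| 300 in the intervention period only | 0 | 300 | not estimable |
| 300 spread over two periods | 129 | 171 | 1.64 |
| 300 spread over three periods | 82 | 109 | 2.05 |
| Year 2 Quarter 3 survey also carries the items, at 65.2% response | 225 | 300 | 1.24 |

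The first row is the only one that follows the stated timing of the acceptability survey. The next two spread the 300 against that timing. The last assumes both content and response for a survey that the SAP does not size.

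**Selection.** Assume 20% initiation, no true effect, and response unrelated to initiation at baseline. Let initiators in the intervention period have 1.5 to 2 times the odds of responding. With response rates r1 (initiators) and r0 (others), solve 0.20·r1 + 0.80·r0 = R under that odds ratio; the completers' initiation rate is 0.20·r1/R.
- R = 65%: 22.2% to 23.5%, a false jump of 2.2 to 3.5 points.
- R = 37%: 24.2% to 27.2%, a false jump of 4.2 to 7.2 points.

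None of these assumptions comes from the SAP. The jump also needs baseline completers: in the first row of the table no adjusted contrast exists, so no false jump can appear.

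**Effect on the quantity the pilot is meant to deliver.** The SD of a binary outcome is √(p(1 − p)).
- All women, p = 0.20: √0.160 = 0.400.
- Completers, p = 0.222: √0.173 = 0.416, which is 4% higher.
- Completers, p = 0.272: √0.198 = 0.445, which is 11% higher.

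This error would arise only in an optional analysis restricted to survey completers. The SD from the EMR extract of all CGW does not change.

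**The case for a change.** The strongest argument for a change is that choosing covariates and the set of women analysed is the business of an SAP, and this one names both the covariates and a source that cannot cover the sample. A pilot SD taken from self-selected responders would pass straight into the design of the larger trial. The comparison of initiation and persistence by partner status is a firm commitment and rests on the same source. The remedy would be only a little wording.

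Part of this stands. The figures are right, surveys are the only source named, and the SAP does not make clear whether the covariate sentence covers the pilot. The dates in the RDD paragraph and the sizing of a preliminary RDD keep that reading open.

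The step from there to harm does not stand:
- The sentence promises to consider covariates, in a run of text about the full-scale trial, for which 300 and 1,265 are not the sample sizes.
- The complete-case model has to be supplied by the reader.
- The 300 belongs to one acceptability survey. The SAP speaks of surveys in the plural and plans a patient-reported measure in Year 2 Quarter 3.
- The medical record may hold some of these items.
- The comparison by partner status is descriptive. It will be made among women whose partner status is known, with that number as its denominator.

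**Conclusion.** No change to the plan is needed. On the stated data, coverage of income and partner status is 24% of the RDD women, or 37% at the first cutoff. That would make an adjusted analysis 1.64 to 2.05 times less precise in standard error, or impossible if all completers fall in the intervention period. These figures apply only if the sentence governs the pilot, if no other survey or the medical record supplies the items, and if the analyst restricts to complete cases. The SAP states none of the three.

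The gap is also of a kind that corrects itself. Once the data are assembled, covariates absent on one side of the cutoff cannot be used for adjustment there, and the analyst will fall back on an unadjusted analysis or on variables held for all periods. The pilot tests no effectiveness, and its unadjusted SDs for the outcomes extracted for all CGW stay sound whatever is decided about income and partner status. The absent coverage figures and missing-covariate rule are details that an analyst of an exploratory pilot can settle sensibly.

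### Does calling 345, 460 and 460 women adequate for the preliminary RDD fail for outcomes measured only in PrEP initiators?

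*SAP*

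**What the plan says.** After quoting sample sizes of 1078, 150, 68 and 109 from a published power study, among them "a sample of 150 would have a power of .80 for detecting a medium effect size" and "a sample of 68 would have a power of .80 for detecting a large effect size", the closing sample-size paragraph of the SAP concludes: "Based on their study, we will recruit an adequately sample size of CGW participants for the preliminary RDD analysis". The planned numbers are "460 CGW participants during the intervention period, an additional 345 CGW participants in the baseline, and 460 in the discontinuation period". The same paragraph says that effectiveness is not being tested at this stage and that "our numbers should allow for calculation of standard deviations to prepare for our fully powered trial".

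Table 1 lists four measures of initial effects. Two are confined to initiators: "Of CGW who initiate PrEP, % adherence at 1 month" and "Of CGW who initiate PrEP, >75% will persist" for at least one month. Initiation among eligible women is a third measure, given without an expected rate. The table notes that these measures serve feasibility of data collection and calculation of standard deviations. Under Measures & Analysis, initial-effects data are to be extracted in all three periods, although the adherence and persistence rows of Table 1 give only Year 3, Quarter 2 as the time of evaluation.

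The analysis text that follows Table 1 plans a descriptive summary of the Table 1 outcomes, a comparison of initiation and persistence by key characteristics, an exploratory logistic regression, and an exploratory RDD meant to improve estimates of standard deviations.

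**The concern.** The sample is called adequate on a count of all women, while two of the four initial-effects measures exist only for those who start PrEP. If few do, the usable sample could fall below the benchmarks that the SAP itself cites, and the adequacy sentence carries no qualifier.

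Two things would be at stake. Standard deviations carried into the full-scale trial could rest on a few dozen women and not on hundreds. And the comparison and regression of persistence could rest on a handful of women who stopped, with their results over-read.

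**Working it through.** **Inputs from the SAP.** Women per period: 345, 460, 460. Quoted sizes: 68 (large effect, power .80), 109 (large, .95), 150 (medium, .80), 1078 (small, .80), all at one-tailed α = .025. Persistence target: 75%. Initiation rate: none given, so 5% to 50% is my assumed range.

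**1. What the quoted sizes mean.** Assume f² = 0.02, 0.15 and 0.35 for small, medium and large effects, and a normal assignment variable cut at its mean. The RDD then needs 1/(1 − 2/π) = 2.752 times the total of a randomised trial. The noncentral-F totals for a randomised trial are 395, 55, 25 and, for a large effect at power .95, 40. Multiplied by 2.752 they give 1087, 151, 69 and 110, against the quoted 1078, 150, 68 and 109. Agreement within about 1% indicates that the quoted figures are totals across one cutoff, so the natural base is two adjacent periods.

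**2. Initiation rate needed.** Rate = quoted size / women in the contrast. This treats all women as eligible and averages the rate over the periods.

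| Contrast | Women | for 68 | for 109 | for 150 |
|---|---|---|---|---|
| Baseline + intervention | 345 + 460 = 805 | 8.4% | 13.5% | 18.6% |
| Intervention + discontinuation | 460 + 460 = 920 | 7.4% | 11.8% | 16.3% |
| All three pooled | 1265 | 5.4% | 8.6% | 11.9% |

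The quoted 1078 exceeds both 805 and 920, so neither two-period contrast meets it even if every woman counts. The SAP therefore cannot be treating every quoted size as a requirement.

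**3. Expected initiators under assumed rates.**

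| Initiation rate | of 805 | of 920 | of 1265 |
|---|---|---|---|
| 5% | 40.3 | 46 | 63.3 |
| 10% | 80.5 | 92 | 126.5 |
| 20% | 161 | 184 | 253 |
| 50% | 402.5 | 460 | 632.5 |

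In the two-period contrasts, 5% misses 68, 10% passes 68 but not 150, and 20% passes both.

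**4. Persistence by characteristic.** With 75% persisting and two equal groups among n initiators, the 95% half-width of a difference is 1.96 × √(2 × 0.75 × 0.25 / (n/2)). The SAP does not say which periods enter this analysis, so both readings are shown.

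| Initiation rate | 460 women: n, non-persisters, half-width | 1265 women: n, non-persisters, half-width |
|---|---|---|
| 5% | 23, 5.8, ±35 points | 63.3, 15.8, ±21 points |
| 10% | 46, 11.5, ±25 | 126.5, 31.6, ±15 |
| 20% | 92, 23, ±18 | 253, 63.3, ±11 |
| 50% | 230, 57.5, ±11 | 632.5, 158.1, ±7 |

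**5. Standard deviations.** If adherence is analysed as continuous, the 95% limits of its SD, from √((n − 1)/χ²), are −23%/+42% at n = 23 and −8%/+10% at n = 230. Persistence is yes/no, so its SD follows from the proportion: √(0.75 × 0.25) = 0.433 at the target.

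**The case for a change.** The strongest case for a change is that the SAP chose to support its adequacy sentence with power figures, and the pilot label does not remove that. Table 1 gives SD calculation as the purpose of the initial-effects measures, the RDD is introduced for the same purpose, and the data are to be extracted in all three periods. It is therefore reasonable to infer that adherence and persistence fall within the RDD. Setting the RDD aside, the persistence regression is planned for this pilot, and at 5% initiation in the intervention period it would have about six non-persisters. Partner status is mentioned only as a survey item, and about 300 surveys are expected, which could shrink that comparison further. A few added sentences would cost little.

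Part of this stands. The denominators differ, and a reader should not carry the word adequate over to initiator-only outcomes. The rest is weaker. That these outcomes belong to the RDD is an inference, and their Table 1 rows give a single evaluation time. The SAP adopts none of the quoted sizes as a target, so measuring it against 150 is the critic's choice. The lowest event counts combine the lowest assumed rate with the intervention period alone, a limit the SAP does not set. The partner-status point further assumes that the EMR lacks the item and that survey respondents initiate at the same rate as other women. A cap on predictors is a preference for a model that the SAP calls exploratory.

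**Conclusion.** No change follows. No figure in the SAP is shown to be wrong. The statement about standard deviations claims only that they can be calculated, with no stated precision, and that holds with any reasonable number of initiators. For outcomes measured on all women, 805 and 920 are well above 150. For adherence and persistence, adequacy is undetermined: at two-period thresholds of about 7% to 8% (for 68) and 16% to 19% (for 150), it depends on an initiation rate that the pilot itself sets out to measure. An expected rate may also properly sit in the protocol, which I have not seen.

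Analysts will fill the gap as a matter of course. The Table 1 definitions already fix initiators as the denominator for both outcomes, and the planned descriptive summary will show how many there are. Anyone planning the full-scale trial will then see how much information each estimate carries. Limiting the adequacy sentence, or adding an expected number, would alter no enrolment, data collection or result in a descriptive pilot that disclaims effectiveness testing.

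This conclusion assumes that results are reported with their denominators and that the persistence model is read as exploratory. The thresholds assume that all recruited women are eligible; if only some are, the rate needed among eligible women is higher.
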